10.0 DATA COLLECTION

See appendix IV for Case Report Forms & patient questionnaires.

11.0 STATISTICAL CONSIDERATIONS

11.1 OVERVIEW: This study's primary goal is to determine the rate of acute and late grade 3-5 gastrointestinal and genitourinary toxicity following CyberKnife treatment, and to estimate efficacy, measured as 5-year bDFS. Per RTOG/ECOG, acute toxicity will be defined as occurring within 90 days of completing treatment. Late toxicity will be defined as toxicity occurring more than 90 days after treatment. It is graded based on Common Terminology Criteria for Adverse Events (CTCAE) v3.0.(see appendix V).

11.2 SAMPLE SIZE:

11.2.1 PRIMARY SAFETY OBJECTIVE: The study is designed to test the null hypothesis that the acute and late GI/GU toxicity rate 5 years following treatment is greater than 10% versus the alternative hypothesis that the toxicity rate is less than or equal to 10%. The sample size is determined such that there is 90% probability, or power, of identifying excessive toxicity if the true toxicity rate is 20% at the one-sided 5% significance level. 101 patients must then be accrued and followed for 5 years, assuming no patients excluded or lost to follow-up. Since the treatment volume for intermediate risk patients is larger than for low-risk patients, the study will be powered to assess toxicity for both subgroups. Additional enrollment for ineligible patients, or lost to follow-up: Since performing central review of pathology prior to enrollment is impractical, some patients will be upgraded, and thus made ineligible. In RTOG 77-06, central review upgraded about 8% of Gleason 2-6 patients to Gleason 7-10⁷⁵. If we assume a similar rate of upgrading, and anticipate 8% additional ineligible/lack-of-data cases, sample size must be

- increased by 1/(0.92*0.92) = 119.33. Thus 120 patients are required to establish acceptable toxicity for each risk cohort.
- 11.2.2 PRIMARY EFFICACY OBJECTIVE: For the low-risk cohort, the study is powered to compare 5-year bDFS rates observed with CyberKnife to 5-year bDFS rates reported with dose-escalated external beam RT. In Beaumont's monotherapy HDR series treating LR patients, 5-yr ASTRO bDFS was 98%; in Demanes' series of 75% LR and 25% IR, this was 96%. We would expect Phoenix outcomes to be slightly higher than ASTRO outcomes at 5 years. Since CK delivers doses similar to HDR monotherapy, a conservative estimate of the success rate for CK is 97.5% for LR patients. In LR patients, prospective studies from Memorial Sloan Kettering⁷⁶ (203 patients, 81Gy) and MD Anderson⁷⁷ (32 patients, 78Gy) demonstrated 5-vr bDFS (Phoenix definition) of 92% and 93%, respectively. Thames' 9-institution review of 231 dose-escalated (70-76Gy) LR patients reported 94% 5-yr Phoenix bDFS. Thus, an objective performance criteria (OPC) for lowrisk patients treated with dose-escalated external beam RT is 93% 5-yr bDFS. Assuming the CK success rate is 97.5%, to test superiority of CK against this OPC with 80% power at the 1-sided 5% significance level will require 150 patients. Increasing the sample size by 1/(0.92*0.92) for ineligible/lack-of-data cases yields 177.22; the required sample size for low-risk patients is 178 patients.
- 11.2.3 TOTAL AND RELATIVE ENROLLMENT OF RISK GROUPS: Per sections 11.2.1 11.2.2, enrollment of 178 low-risk patients are required to compare the 5-year bDFS rate observed with CyberKnife to the 5-year OPC rate, and 120 intermediate risk patients are required to establish acceptable toxicity for each risk cohort. CaPSURE data showed a ratio of low to intermediate risk patients, using D'Amico's definition⁷⁸, of 46.8%:37.2%. This CK protocol excludes intermediate risk patients with both PSA 10-20ng/ml and Gleason 7 histology. Based on proportions of patients in these subgroups reported in Partin's⁷⁹ study, this would exclude 12% of intermediate risk patients. Combining these proportions, we would expect a ratio of low to intermediate risk patients of 1.43: 1. Thus we would expect 172 low-risk patients enrolled by the time 120 intermediate risk patients have been enrolled. Each cohort will be closed to accrual once requisite enrollment is achieved: 178 low-risk patients, and 120 intermediate risk (298 total patients)
- 11.2.4 ACCRUAL RATE: the initial three months while institutions are obtaining IRB approval, therefore we do not expect to meet the targeted monthly accrual rate until after the first three months. The estimated accrual rate is 2.5 patients per study site per month. Expectations of 10 treating study sites assume an accrual period of approximately 11 months, or 14 month total
- 11.2.5 INTERIM ADJUSTEMENT IN ENROLLMENT: Interim analysis of the first 200 enrolled patients showed that 13 were actually ineligible because they were taking finasteride or dutasteride. Enrollment will thus be increased by 13 patients. Exclusion of patients on 5-alpha reductase inhibitors is clarified in section 5.12. We recognize that LHRH agonist/antagonist (e.g. leuprolide, goserelin, triptorelin, degarelix), hormone (e.g. DES), or peripheral blocker (e.g. flutamide, bicalutamide, nilutamide) administration given more than two months before enrollment may impact efficacy. Thus sample size (section 11.2) will be increased to insure enrollment is sufficient to achieve study objectives for the subgroup of patients naïve to such therapy. Interim analysis of the first 200 enrolled patients showed

 \Box

four had received LHRH agonists or peripheral hormone blockers. We could expect four more such patients to be enrolled through completion of the study. Thus enrollment should be increased by an additional eight patients, or 21 patients total. Applying the proportion of low to intermediate risk patients described in section 11.2.3, total enrollment will be increased to 129 intermediate-risk, and 190 low-risk (319 patient total). If subsequent interim evaluations show the estimated proportion of ineligible/lack-of-data cases is inaccurate, required enrollment will be accordingly adjusted.

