2.0 OBJECTIVES

PRIMARY OBJECTIVES: The primary safety goal of this study is to estimate, in both low-risk and intermediate-risk cohorts, the rates of acute and late grade 3-5 gastrointestinal and genitourinary toxicity observed during the five years following CyberKnife SRS for prostate cancer. The primary efficacy goal is to document the rate of biochemical Disease-Free Survival (bDFS), Phoenix and ASTRO definitions, at 5 years.

SECONDARY OBJECTIVES: to measure the following in the study population: Rates of local failure, distant failure, disease-free survival, disease-specific survival, and overall survival; quality of life (QOL) in generic and organ-specific domains; work effort required in treatment planning and delivery of CyberKnife SRS.

Patients will be followed annually to 10 years, to collect additional data for descriptive analysis.

3.0 **DEVICE**

Accuray, Inc. (Sunnyvale, CA), received FDA clearance in July 1999 to provide treatment planning and image guided stereotactic radiosurgery and precision radiotherapy for lesions, tumors and conditions of the brain, base of skull and cervico-thoracic spine, head and neck using the CyberKnife. On August 10, 2001, Accuray, Inc. received 510(k) FDA clearance (510(k) number K011024) to provide treatment planning and image-guided stereotactic radiosurgery and precision radiotherapy for lesions, tumors, and conditions anywhere in the body when radiation treatment is indicated.

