11.4 STATISTICAL METHODS

11.4.1 PRIMARY ENPOINTS

11.4.1.1 SAFETY: The upper limit of a one-sided 95% confidence interval for the expected proportion of patients experiencing a Serious Adverse Event (SAE) is estimated by U, where

$$U = \frac{(2np + Z_{0.05}^2) + Z_{0.05}\sqrt{Z_{0.05}^2 + 4pn(1 \cdot p)}}{2(n + Z_{0.05}^2)}$$

Here "p" is the observed proportion of patients experiencing an SAE . The CyberKnife intervention will be considered to be safe if this study's result verifies that U is not above $20\%^{80}$.

11.4.1.2 EFFICACY: The lower limit of a one-sided 95% confidence interval for the expected proportion of patients experiencing biochemical disease-free survival (bDFS) is estimated by L, where

$$L = \frac{(2np + Z_{0.05}^2) \cdot Z_{0.05} \sqrt{Z_{0.05}^2 + 4pn(1 \cdot p)}}{2(n + Z_{0.05}^2)}$$

Here "p" is the observed proportion of patients experiencing bDFS in either

ACCP001.4

arm of the trial. The CyberKnife intervention will be considered to be effective if this study's result verifies that L is not below 93%.

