- Adverse Events: An unanticipated adverse effect is defined by the FDA as any serious adverse effect on health or safety or any life-threatening problem or death caused by, or associated with, a device, if that effect, problem, or death was not previously identified in nature, severity, or degree of incidence in the protocol (including a supplementary plan), or any other unanticipated serious problem with a device that relates to the rights, safety, or welfare of subjects. Should any unanticipated adverse device effects occur during the course of the study, the clinical monitor will ensure that they are documented by the investigator and reported to the sponsor and the reviewing Institutional Review Board (IRB) as soon as possible, but no later than ten working days after the investigator first learns of the effect(s). The report regarding any unanticipated adverse device effect also will be provided to all other IRBs for the sites at which this clinical evaluation is being conducted. The clinical monitor, on behalf of the sponsor, will work with one of the lead site's investigators and Accuray's medical monitor to conduct an evaluation of such effects. Following this evaluation, if the determination is made that an unanticipated adverse effect presents an unreasonable risk to subjects, the clinical evaluation will be paused, if deemed appropriate

(to enable further investigation) or terminated as soon as possible. Termination shall occur no later than five working days after the sponsor makes the determination and no later than 15 working days after the sponsor receives notice of the unanticipated adverse device effect. In the event of termination, IRB approval will be obtained prior to resuming the clinical evaluation.

12.5 Below are criteria for early termination of either arm of the trial should an excessive number of patients experience a Serious Adverse Event (SAE). This depends upon the number so far enrolled and a criterion that identifies too high a rate. The stopping criteria differ after 48, 96 and 120 patients have been enrolled in both groups with additional applications when up to 144 and 178 have been enrolled in the low-risk group. Consistent with Section 11.2.1, we define an observed SAE rate of 20% as too high The statistical requirement is that for up to "m" patients enrolled, the number of observed SAEs must be few enough so that there is a 95% chance that the "true" rate does not exceed 20%.

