	Serious Adverse Event (SAE) Stopping Criteria					
Participants to	Independently for both low- and interm-risk arms, stop an arm if					
be enrolled: 298	the number of grade 3-5 effects for that arm equals or exceeds:					
(178 low-risk,	Enrollment 1-48: 6 SAEs					
120 interm-risk)	Enrollment 1-96: 14 SAEs					
	Enrollment 1-120: 18 SAEs					
	Enrollment 1-144: 22 SAEs					
	Enrollment 1-178: 28 SAEs					

12.6 Regulatory Reporting: Any reports regarding safety issues and potential safety issues will also be provided to Accuray's Regulatory Affairs Department. Such reports will be evaluated and reported to the FDA and all applicable regulatory agencies, as deemed required.

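### The safety hypotheses in section 11.2.1 run opposite to their own power statement, and the decision rule in section 11.4.1.1 tests a different ceiling on a differently named event

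*Combined protocol and SAP*

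**What the plan says.** All references are to the combined protocol and SAP.

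- **Section 2.0** sets the primary safety goal as estimating "the rates of acute and late grade 3-5 gastrointestinal and genitourinary toxicity observed during the five years following CyberKnife SRS", in both risk cohorts. Section 11.1 names the same grade 3-5 GI/GU endpoint.
- **Section 11.2.1** tests "the null hypothesis that the acute and late GI/GU toxicity rate 5 years following treatment is greater than 10% versus the alternative hypothesis" that the rate is 10% or lower, and gives no grade. It then sizes the study for "90% probability, or power, of identifying excessive toxicity if the true toxicity rate is 20% at the one-sided 5% significance level" and concludes that "101 patients must then be accrued and followed for 5 years", inflated to 120 per risk cohort.
- **Section 11.4.1.1** computes U, the upper limit of a one-sided 95% interval (the Wilson score form), where p "is the observed proportion of patients experiencing an SAE". The intervention is called safe if the "result verifies that U is not above" 20%.
- **Section 12.5** states: "Consistent with Section 11.2.1, we define an observed SAE rate of 20% as too high". Its table stops an arm when "the number of grade 3-5 effects for that arm equals or exceeds" the tabulated count.

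**The concern.** One primary endpoint has three set-ups:

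- (a) the printed hypotheses: null above 10%, alternative at most 10%;
- (b) the power sentence and sample size: null at most 10%, with power to show harm at 20%;
- (c) the decision rule: null at least 20%, alternative below 20%.

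The printed 90% and 5% describe (b), but the verdict will come from (c), and no planned analysis tests 10%. Under section 11.2.1 as printed, a finding of safety means that a rate above 10% was rejected. Under section 11.4.1.1 it means only that 20% was excluded. The event also moves between grade 3-5 GI/GU toxicity, GI/GU toxicity of unstated grade, SAEs of any kind, and grade 3-5 effects that the table does not tie to patients. If ceiling and numerator are left open, they could be chosen once the data are known.

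**Working it through.** **Inputs.** From section 11.2.1: 10%, 20%, one-sided 5%, 90% power, n = 101. From section 11.4.1.1: the formula for U and the 20% ceiling. From section 11.2.2: 150 evaluable low-risk patients. Assumption: the same event, counted once per patient, is used throughout.

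**1. Reproducing 101.** One-sample binomial, normal approximation:

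n = [(z_α √(p0 q0) + z_β √(p1 q1)) / (p1 − p0)]²

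- p0 = 0.10, p1 = 0.20: [(1.645 × 0.3 + 1.2816 × 0.4) / 0.1]² = 101.2, the plan's figure. Inflation: 101 / (0.92 × 0.92) = 119.33, so 120.
- p0 = 0.20, p1 = 0.10 (the direction of section 11.4.1.1): 108.7, so 109.

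The sample size therefore belongs to (b).

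**2. Can the 90% belong to the printed hypotheses?** Rejecting a rate above 10% with 101 patients requires U at or below 10%, that is, at most 5 events. At a true 20% the probability of 5 or fewer is about 0.002%. It cannot.

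**3. Cut-offs.** U = [2np + z² + z √(z² + 4np(1 − p))] / [2(n + z²)], with z = 1.645 and z² = 2.706. For 13 of 101: [26 + 2.706 + 1.645 × √(2.706 + 52 × 0.8713)] / (2 × 103.706) = 40.10 / 207.41 = 19.3%. For 14 of 101, U = 20.5%.

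| Set-up | 101 evaluable | 150 evaluable |
|---|---|---|
| (a) rejects a rate above 10% | at most 5 (U 9.8%; 6 gives 11.1%) | at most 8 (U 9.2%; 9 gives 10.04%) |
| (c) declares safe, U ≤ 20% | at most 13 (U 19.3%) | at most 21 (U 19.3%; 22 gives 20.04%) |
| (b) shows excess over 10% | at least 16 | at least 22 |

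For (b), the exact level and power at 20% are 4.3% and 88.1% with 101, and 4.4% and 96.3% with 150.

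So 6 to 13 of 101, or 9 to 21 of 150, would be called safe while the printed null stands. With 101 patients, 14 or 15 events are neither safe under (c) nor excessive under (b).

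**4. Operating characteristics of the actual rule (c)**, exact binomial, before the stopping rule in section 12.5:

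| True rate | P(declared safe), n = 101 | n = 150 |
|---|---|---|
| 10% | 86.9% | 95.6% |
| 15% | 33.2% | 42.0% |
| 20% | 4.3% | 3.7% |

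**5. Power if U must not exceed 10%**, exact binomial, at assumed true rates:

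| True rate | n = 101 (at most 5) | n = 150 (at most 8) |
|---|---|---|
| 3% | 91.6% | 96.2% |
| 5% | 60.7% | 66.4% |
| 7% | 28.2% | 27.0% |

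**The case against.** The strongest reply is that the protocol contains only one rule for declaring safety, the one in section 11.4.1.1. Section 11.2.1 is a sample-size paragraph, and the cut-offs of 5 and 16 events are inferred from it. On that reading 20% is a coherent ceiling: section 11.2.1 treats a true 20% as excessive, and sections 11.4.1.1 and 12.5 both use it, so the stray element is the 10% in the hypothesis sentence. False reassurance at 20% is held below 5%. The stated goal is to estimate the rate, so readers would see the estimate and its limit in any case. The event is partly bridged too, because section 11.1 supplies the grade just above section 11.2.1 and the SAE table in section 12.5 counts grade 3-5 effects.

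Much of this is fair. Protection at 20% is real, the gap at 14 to 15 events is not a contradiction in itself (it disappears with 150 patients), and 20% may well be what was meant. But reversing the printed hypotheses would not settle the matter, since section 11.4.1.1 would still test 20% and the 90% would still describe another test. The stopping table does not define the numerator in section 11.4.1.1 or restrict it to GI/GU events. The plan also goes beyond estimation: it states hypotheses and a pass/fail verdict.

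**Conclusion.** The concern holds and should be corrected before the primary safety analysis. The figure of 101 is right for a null of at most 10% against 20%, but that test is neither the one printed nor the one that decides. The consequence is interpretive: 6 to 13 events in 101, or 9 to 21 in 150, would be labelled safe with an upper limit between about 10% and 19.3%, although section 11.2.1 presents safety as a rate no higher than 10%. The power of the rule that will be applied is 86.9% with 101 evaluable at a true 10%, not 90%.

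These figures assume one per-patient event throughout and take no account of stopping under section 12.5. The true rates used for power are assumptions, because the documents give no planning rate.

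**What to change.** The sponsor should state which ceiling and which event are intended, and align sections 11.2.1, 11.4.1.1 and 12.5. For the event, one per-patient definition should be used throughout; sections 2.0 and 11.1 already name grade 3-5 GI/GU toxicity.

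**Option A, 20% kept.** Suggested text: null, the proportion of patients with the named event within 5 years is at least 20%; alternative, below 20%; one-sided 5%; safe if U ≤ 20%. The conclusion is then worded as below 20%. Replace the 90% statement with the power to declare safety at an assumed true 10%: about 87% with 101 evaluable and 96% with 150. Say that this is a different quantity from detection at a true 20%, and that it is before section 12.5. State also whether a stopped arm can still be declared safe. If it cannot, an illustrative calculation at a true 10%, with the section 12.5 bounds applied to evaluable patients, gives about 85% (n = 101) and 93% (n = 150) if half of the five-year events fall within their enrolment block. The extreme case, with all events inside it, gives about 63% for both.

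Cost: wording only, with no extra patients and no change of rule. If 90% power is wanted for the 101-patient cohort, the normal approximation gives 109 evaluable (109 / 0.8464 = 128.8, so 129 enrolled). Exact power is 87.3% at 109 and 91.0% at 120 evaluable. The 129 intermediate-risk patients in section 11.2.5 do not supply this, because that increase covers ineligible and hormone-exposed patients.

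**Option B, a claim of at most 10%.** The rule becomes U ≤ 10%: at most 5 of 101 or 8 of 150. No patients are added, but power depends heavily on the true rate, from about 92% and 96% at 3% to about 28% and 27% at 7%. The nearest figure in the documents, section 1.11's series with no grade 3 or 4 toxicity in 26 patients at 18 months, has an exact one-sided 95% upper limit of 1 − 0.05^(1/26) = 10.9%, so it does not separate these cases.

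If set-up (b) was intended, the hypotheses are reversed, 101 and 120 stand, and section 11.4.1.1 must become a test against 10%. Failing to reject would then not demonstrate safety.

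### Section 11.2.5 projects four further hormone-exposed men where its own rate gives about two, and splits all 21 replacements by a forecast accrual ratio instead of by the cohort that lost the men

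*Combined protocol and SAP*

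**What the plan says.** Section 11.2.3 sets enrollment at 178 low-risk and 120 intermediate-risk men, 298 in all, and closes each cohort separately when its number is reached. From two outside series it forecasts the accrual mix: "we would expect a ratio of low to intermediate risk patients of 1.43: 1".

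Section 11.2.5 then reports two findings.

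- Men on 5-alpha-reductase inhibitors: "Interim analysis of the first 200 enrolled patients showed that 13 were actually ineligible because they were taking finasteride or dutasteride". The response is one for one: "Enrollment will thus be increased by 13 patients".
- Men given other hormone therapy more than two months before enrollment: "four had received LHRH agonists or peripheral hormone blockers". The plan wants enough men without such exposure to meet the study objectives. It continues: "We could expect four more such patients to be enrolled through completion of the study". It adds the four found to the four projected: "Thus enrollment should be increased by an additional eight patients, or 21 patients total".

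The 21 are allocated in one step: "Applying the proportion of low to intermediate risk patients described in section 11.2.3, total enrollment will be increased to 129 intermediate-risk, and 190 low-risk". The total becomes 319, which the Schema repeats. The section gives no basis for the projected four and does not report the risk cohort of the 13 or of the 4.

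**The concern.** There are two separate problems.

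First, the projection is worded as an expectation, but it equals the count from the first 200 men although far fewer than 200 remained. The plan's own rate supports about half that number.

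Second, the 1.43:1 ratio is a pre-trial forecast of who would enroll. It is a reasonable way to place men not yet seen. But 17 of the 21 additions (13 + 4) replace men already in the trial, and section 5.4 requires every man to belong to a risk group. Low-risk efficacy and safety in each cohort have separate sample-size requirements, so a loss in one cohort is not made good by an extra man in the other. If the 17 fell mainly in one cohort, that cohort is under-replaced and the other is over-enrolled.

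**Working it through.** **Inputs.** Section 11.2.5: 200 men reviewed, 13 ineligible, 4 hormone-exposed, 4 projected. Section 11.2.3: 178 + 120 = 298 and the ratio 1.43:1. Section 11.2.1: 101 evaluable men per cohort (10% against 20%, 90% power, one-sided 5%). Section 11.2.2: 150 evaluable low-risk men (93% against 97.5%, 80% power, one-sided 5%). Both sections retain 0.92 × 0.92 = 0.8464.

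**The plan's own figures.**

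- Total: 298 + 13 + 4 + 4 = 319.
- Split: 21 × 1.43/2.43 = 12.4, rounded to 12; 21/2.43 = 8.6, rounded to 9. Hence 178 + 12 = 190 and 120 + 9 = 129, as stated.
- Base sizes: n = [(1.645·√(p0(1−p0)) + z·√(p1(1−p1))) / (p1−p0)]², with z for the stated power, gives 101.2 (stated 101) and 149.97 (stated 150). Also 101/0.8464 = 119.33 and 150/0.8464 = 177.22, as stated.

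Only the projected four does not reproduce.

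**Projection.** The rate is 4/200 = 2%.

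| Final total | Men after the first 200 | Expected further men |
|---|---|---|
| 298 | 98 | 1.96 |
| 311 | 111 | 2.22 |
| 319 | 119 | 2.38 |

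Four more at 2% would need 4/0.02 = 200 further men. With two, the increase is 13 + 4 + 2 = 19 and the total 317. With three (rounding up), it is 20 and 318.

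**Slack in the base sizes.** 178 × 0.8464 = 150.7 against 150, and 120 × 0.8464 = 101.6 against 101.

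**Split.** Take 19 losses (17 found and 2 expected), of which k are low risk. Following the plan's own accounting, subtract them from 190 and 129 and then apply 0.8464.

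- Low risk: (190 − k) × 0.8464 ≥ 150 requires k ≤ 12.
- Intermediate risk: (129 − 19 + k) × 0.8464 ≥ 101 requires k ≥ 10.

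Power by the same normal formula:

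| k low risk of 19 | Low-risk evaluable | Efficacy power | Intermediate evaluable | Safety power |
|---|---|---|---|---|
| 0 | 160.8 | 83.3% | 93.1 | 88.1% |
| 9 | 153.2 | 81.0% | 100.7 | 89.9% |
| 10 | 152.4 | 80.8% | 101.6 | 90.1% |
| 12 | 150.7 | 80.2% | 103.3 | 90.4% |
| 13 | 149.8 | 79.9% | 104.1 | 90.6% |
| 19 | 144.7 | 78.2% | 109.2 | 91.6% |

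With four further losses (21 in all) the two worst cases are 77.6% and 87.6%.

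**Ineligible men only.** The table removes the hormone-exposed men, so it describes the hormone-naive subgroup. Section 5.12 excludes hormone use only in the two months before enrollment or during treatment, so men exposed earlier remain eligible. Removing only the 13 ineligible men:

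- all 13 low risk: (190 − 13) × 0.8464 = 149.8, efficacy power 79.9%;
- all 13 intermediate risk: (129 − 13) × 0.8464 = 98.2, safety power 89.3%.

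**The case against.** **The four may be a cautious allowance.** A rate of 4/119 = 3.4% lies inside the exact 95% interval for 4/200 (0.5% to 5.0%). At a true 2%, the chance of four or more is 0.13 with 98 men and 0.22 with 119. The excess is at most 2 of 319 men (0.6%) and protects the study. This stands as far as consequences go. It does not make four the expected number, which is how the plan words it.

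**The losses may be counted twice.** The 0.8464 already allows 8% for ineligible or missing-data cases, and 13/200 is 6.5%. If the 13 belong inside that allowance, the evaluable numbers above are too low. The plan itself adds the 13 on top of the inflated 298, and the working follows it, but this remains an assumption.

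**The plan can correct itself.** Section 11.2.5 ends by promising to adjust enrollment if the assumed share of ineligible or missing-data cases proves wrong. That covers the overall share. It does not address the division between cohorts.

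**Stronger readings that the documents do not support.**

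- A reader might compute exact power under the Wilson rule of section 11.4.1.2 at 143 evaluable low-risk men (all 21 losses low risk), get 71%, and infer a serious loss. That is a step in a discrete rule: four failures are allowed at 143 and five at 144, where exact power is 84.7% (84.3% at 145, 82.5% at the planned 150).
- A reader might infer that hormone-related replacements in the intermediate cohort serve no purpose and should all go to low risk. Section 11.2.5 ties the increase to the study objectives under section 11.2, which powers safety in both cohorts, and section 11.4.1.2 refers to bDFS in either arm.
- A reader might infer that the primary low-risk test has lost its 80% power. Even with all 13 ineligible men low risk, it keeps about 79.9%.

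**Conclusion.** Both points hold, and both are minor.

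The projection should be about two (three if rounded up), so 21 and 319 are overstated by 1 to 2 men, on the safe side.

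The split uses a forecast where the plan could use the recorded risk group of 17 enrolled men. If losses followed 1.43:1, both targets would be met (151.4 and 102.6 evaluable with 19 losses). Outside the range of 10 to 12 low-risk losses out of 19, one cohort misses its target. The miss is at most about two percentage points of power for hormone-naive men, and less than one point when only the ineligible men are removed.

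This rests on the plan's normal formula, its 0.8464 retention applied after the losses are subtracted, and a constant 2% exposure rate. Because the cohort of the 17 men is not reported, the shortfall is a possibility and has not been demonstrated.

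**What to change.** In section 11.2.5:

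1. Change the projected four to about two (or three, rounded up), with the calculation shown, or state that four is a deliberate allowance.
2. Report the risk cohort of the 13 ineligible and the 4 hormone-exposed men, and replace each in the cohort where he was found.
3. Apply 1.43:1 only to the projected men: 2 × 1.43/2.43 = 1.2, so one in each cohort; or 3 × 1.43/2.43 = 1.8, so two low-risk and one intermediate-risk.
4. Restate 190, 129 and 319, and the Schema total. If m of the 17 are low risk and two more men are projected, the targets are 178 + m + 1 low-risk and 120 + (17 − m) + 1 intermediate-risk, 317 in total. With three projected the total is 318.

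The cost is a short text change and a tabulation by risk group of men already enrolled. Total enrollment does not rise.
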